5.2. Exclusion criteria

The following criteria should be checked at the time of study entry. The potential participant MAY NOT be included in the study if ANY exclusion criterion applies:

5.2.1. Medical conditions

- Any confirmed or suspected immunosuppressive or immunodeficient condition resulting from disease (e.g. current malignancy, human immunodeficiency virus) or immunosuppressive/cytotoxic therapy (e.g. medication used during cancer chemotherapy, organ transplantation, or to treat autoimmune disorders), based on medical history, and physical examination (no laboratory testing required).
- History of any reaction or hypersensitivity likely to be exacerbated by any component of the study intervention(s).
- Hypersensitivity to latex.
- Serious or unstable chronic illness.
- Any history of dementia or any medical condition that moderately or severely impairs cognition.
 - Note: If deemed necessary for clinical evaluation, the investigator can use tools such as Mini-Mental State Exam (MMSE), Mini-Cog or Montreal Cognitive Assessment (MoCA) to determine cognition levels of the participant.
- Recurrent or un-controlled neurological disorders or seizures. Participants with
 medically-controlled active or chronic neurological diseases can be enrolled in the
 study as per investigator assessment, provided that their condition will allow them to
 comply with the requirements of the protocol (e.g. completion of the diary cards,
 attend phone call/study site visits).
- Significant underlying illness that in the opinion of the investigator would be expected to prevent completion of the study (e.g. life-threatening disease likely to limit survival up to study end).
- Any medical condition that in the judgment of the investigator would make intramuscular injection unsafe.

5.2.2. Prior/Concomitant therapy

- Use of any investigational or non-registered product (drug, vaccine or medical device) other than the study intervention(s) during the period beginning 30 days before study intervention administration and ending 30 days after study intervention administration, or planned use during the study period.
- Planned or actual administration of a vaccine not foreseen by the study protocol in the period starting 30 days before and ending 30 days after the study intervention administration, with the exception of inactivated and subunit influenza vaccines which can be administered up to 14 days before or from 14 days after the study vaccination.

Note: In case an emergency mass vaccination for an unforeseen public health threat (e.g. a pandemic) is recommended and/or organized by the public health authorities, outside the routine immunization program, the time period described above can be reduced if necessary for that vaccine provided it is used according to the local governmental recommendations and that the Sponsor is notified accordingly.

- Previous vaccination with an RSV vaccine.
- Administration of long-acting immune-modifying drugs or planned administration at any time during the study period (e.g. infliximab).
- Administration of immunoglobulins and/or any blood products or plasma derivatives during the period starting 90 days before the administration of the study intervention or planned administration during the study period.
- Chronic administration (defined as more than 14 consecutive days in total) of immunosuppressants or other immune-modifying drugs during the period starting 90 days prior to the study intervention administration or planned administration during the study period. For corticosteroids, this will mean prednisone ≥ 20 mg/day or equivalent. Inhaled and topical steroids are allowed.

5.2.3. Prior/Concurrent clinical study experience

• Concurrently participating in another clinical study, at any time during the study period, in which the participant has been or will be exposed to an investigational or a non-investigational vaccine/product (drug or invasive medical device).

Note: EEC directive 93/42/EEC defines an invasive medical device as 'A device which, in whole or in part, penetrates inside the body, either through a body orifice or through the surface of the body'.

5.2.4. Other exclusions

- History of chronic alcohol consumption and/or drug abuse as deemed by the investigator to render the potential participant unable/unlikely to provide accurate safety reports or comply with study procedures.
- Planned move during the study period that will prohibit participating in the study until study end.
- Bedridden participants.
- Participation of any study personnel or their immediate dependents, family, or household members.

5.3. Lifestyle considerations

No lifestyle restrictions are applicable for this study.

5.4. Screening failures

Not applicable for this study.

5.5. Criteria for temporarily delaying enrolment/Study intervention administration

Enrolment/study intervention administration may be postponed within the permitted time interval until transient conditions cited below are resolved:

- Acute disease and/or fever at the time of enrolment and/or study intervention administration. Refer to the SoA (Table 1) for definition of fever and preferred location for measuring temperature in this study.
- Participants with a minor illness (such as mild diarrhea, mild upper respiratory infection) without fever may be enrolled and/or dosed at the discretion of the investigator.
- Participants with symptoms suggestive of active Coronavirus Disease 2019 (COVID-19) infection (e.g., fever, cough, etc.). The return of the participant to the site will follow the specific guidance from local public health and other competent authorities (e.g. free of symptoms, COVID-19 negative testing, etc.).
- Participants with known COVID-19 positive contacts may be vaccinated at least 14 days after the exposure, provided that the participant remains symptom-free, and at the discretion of the investigator.
- In case of administration of inactivated and subunit influenza vaccines: Postponement of study vaccine administration within given protocol timelines to allow respect of the 14-days interval between flu vaccination and study vaccine administration.

6. STUDY INTERVENTION AND CONCOMITANT THERAPY

6.1. Study interventions administered

Refer to the Glossary of terms for the definition of study intervention.

Table 6 Study intervention(s) administered

Study group	RSVPreF3_Grp1	RSVPreF3_Grp3	
Study intervention name:	RSVPreF3 OA	RSVPreF3 OA	RSVPreF3 OA
•	investigational vaccine	investigational vaccine	investigational vaccine
Study intervention	RSVPreF3 (120 µg) RSVPreF3 (120 µg)		RSVPreF3 (120 µg)
formulation:	(Lot 1) (Lot 2)		(Lot 3)
	AS01E (Lot A):	AS01E (Lot B):	AS01E (Lot C):
	QS-21* (25 μg), MPL	QS-21* (25 μg), MPL	QS-21* (25 μg), MPL
	(25 μg), liposomes;	(25 µg), liposomes; water	(25 µg), liposomes; water
	water for injections q.s. 0.5 mL	for injections q.s. 0.5 mL	for injections q.s. 0.5 mL
Presentation:	RSVPreF3: Vial; powder	RSVPreF3: Vial; powder	RSVPreF3: Vial; powder
	for suspension for	for suspension for	for suspension for
	injection	injection	injection
	AS01E: Vial; suspension	AS01E: Vial; suspension	AS01E: Vial; suspension
	for suspension for	for suspension for	for suspension for
	injection	injection	injection
Туре:	Biologic	Biologic	Biologic
Route of administration:	IM	IM	IM
Administration site:			
• Location	Deltoid	Deltoid	Deltoid
• Directionality	Upper	Upper	Upper
Laterality**	Non-dominant	Non-dominant	Non-dominant
Number of doses to be	1	1	1
administered:			
Volume to be	0.5 mL	0.5 mL	0.5 mL
administered by dose ***:			
Packaging, labeling and	Refer to the SPM for	Refer to the SPM for more	Refer to the SPM for more
TM:	more details	details	details
Manufacturer:	GSK Biologicals	GSK Biologicals	GSK Biologicals

Grp: group; IM: Intramuscular; SPM: Study Procedures Manual

Study participants must be observed closely for at least 30 minutes after the administration of the study intervention. Appropriate medical treatment must be readily available during the observation period in case of anaphylaxis, syncope.

^{*} QS-21: Quillaja saponaria Molina, fraction 21 (Licensed by GSK from Antigenics Inc., a wholly owned subsidiary of Agenus Inc., a Delaware, USA corporation).

^{**} The non-dominant arm is the preferred arm of injection. In case it is not possible to administer the study intervention in the non-dominant arm, an injection in the dominant arm may be performed.

^{***} Refer to the SPM for the volume after reconstitution.

6.2. Preparation, handling, storage, and accountability

The study interventions must be stored in a secured place within the temperature range specified on the study intervention's label. The storage temperature should be continuously monitored and recorded with a calibrated (if not validated) temperature monitoring device(s).

Only authorized study personnel should be allowed access to the study intervention. Storage conditions will be assessed by a sponsor study contact during pre-study activities. Refer to the SPM for more details on storage and handling of the study intervention(s).

6.3. Measures to minimize bias: randomization and blinding

6.3.1. Participant identification

Participant identification numbers will be assigned sequentially to the individuals who have consented to participate in the study. Each study center will be allocated a range of participant identification numbers.

6.3.2. Randomization to study intervention

Approximately 750 eligible participants will be randomly assigned (1:1:1) to the 3 study groups (250 participants in each study group: RSVPreF3_Grp1, RSVPreF3_Grp2, and RSVPreF3_Grp3) at Visit 1 (Day 1).

The randomization of supplies within blocks will be performed at GSK, using MATerial Excellence (MatEx), a program developed for use in Statistical Analysis System (SAS) (Cary, NC, United States [US]) by GSK. Entire blocks will be shipped to the study centers/warehouse(s).

To allow GSK to take advantage of greater rates of recruitment in this multi-center study and thus to reduce the overall study recruitment period, an over-randomization of supplies will be prepared.

6.3.3. Intervention allocation to the participant

An automated Internet-based system, Source data Base for Internet Randomization (SBIR) will be used for randomization and for identification of intervention material.

The randomization algorithm will use a minimization procedure accounting for age (60 to 69, 70 to 79 or \geq 80 years) and center. Minimization factors will have equal weight in the minimization algorithm. Refer to Section 4.1.2 for the enrolment rules.

The 3 study groups for the lot-to-lot evaluation will receive adjuvanted vaccine consisting of unique combinations of RSVPreF3 antigen lots, i.e., Lot 1, Lot 2, or Lot 3, and extemporaneously reconstituted with AS01_E adjuvant lots, i.e., Lot A, Lot B, and Lot C.

217131 (RSV OA=ADJ-009) Protocol Final

One of the combinations of the $AS01_E$ adjuvant lot and RSVPreF3 antigen lot will be in alignment with the RSV OA=ADJ-006 study (efficacy study). The 2 remaining adjuvant lots will be randomly combined with the 2 RSVPreF3 antigen lots. The random assignment will be done using the RAND function, that uses the Mersenne-Twister algorithm. Details of the study groups and antigen/adjuvant lots are presented in Table 5 and Table 6.

Once a participant identification number is allocated, the randomization system will determine study group and will provide the study intervention number to be used.

When SBIR is not available, please refer to the SBIR user guide or SPM for specific instructions.

Refer to the SPM for additional information relative to the intervention number allocation.

6.3.4. Blinding and unblinding

Data will be collected in a double-blind manner. The investigator and the participant will not know which lot of the study intervention is administrated.

The laboratory in charge of sample testing will be blinded to the study intervention lot assignment. Codes will be used to link the participant and study to each sample. There will be no link between the study intervention groups and the identity of the participant.

The study will be conducted in a double-blind manner from study start-up to final analysis, beyond which the study will be considered single-blind. The study participants will remain blinded up to study end, however, the investigators will receive a copy of the Clinical Study Report (CSR) with results of the final analyses on immunogenicity and safety data up to Day 31. As a consequence, the investigators could become unblinded to some specific participants through summary results. The individual data listings and participant treatment assignments will not be provided to the investigators until after the conclusion of the study (completion of Month 6 contact [study end]).

Note that the GSK central study team (Clinical Research and Development Lead [CRDL], Statistician, Safety Representative, etc.) will be unblinded to the study intervention lot assignment at the time of final analysis in order to prepare the CSR of the final analysis.

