10.1.5. Committees structure

GSK will obtain favorable opinion/approval to conduct the study from the appropriate regulatory agency, in accordance with applicable regulatory requirements, prior to a site initiating the study in that country. This includes IRBs/IECs for review and approval of the protocol and subsequent amendments, ICF and any other documentation.

217131 (RSV OA=ADJ-009) Protocol Final

Safety oversight will be provided by a blinded SRT composed of GSK RSV OA project team members

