10.1.6. Dissemination of clinical study data

The key design elements of this protocol and results summaries will be posted on www.ClinicalTrials.gov and/or GSK Clinical Study Register in compliance with applicable regulations/GSK policy. GSK will aim to register protocols summaries prior to study start and target results summaries submission within 12 months of primary/ study completion date. Where external regulations require earlier disclosure, GSK will follow those timelines.

Where required by regulation, summaries will also be posted on applicable national or regional clinical study registers.

Where required by applicable regulatory requirements, an investigator signatory will be identified for the approval of the study report, and provided reasonable access to statistical tables, figures, and relevant reports. GSK will also provide the investigator with the full summary of the study results. The investigator is encouraged to share the summary results with the study participants, as appropriate.

GSK will provide the investigator with the randomization codes for their site only after completion of the full statistical analysis.

GSK intends to make anonymized patient-level data from this study available to external researchers for scientific analyses or to conduct further research that can help advance medical science or improve patient care. This helps ensure the data provided by study participants are used to maximum effect in the creation of knowledge and understanding.

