10.3.8.2. Assessment of causality

The investigator must assess the relationship between study intervention and the occurrence of each unsolicited AE/SAE using clinical judgment. Where several different interventions were administered, the investigator should specify, when possible, if the unsolicited AE/SAE could be causally related to a specific intervention. When a causal relationship to a specific study intervention cannot be determined, the investigator should indicate the unsolicited AE/SAE to be related to all interventions.

Alternative possible causes, such as the natural history of underlying disease, concomitant therapy, other risk factors, and the temporal relationship of the event to the study intervention will be considered and investigated. The investigator will also consult the IB to assist in making his/her assessment.

217131 (RSV OA=ADJ-009) Protocol Final

Causality should be assessed by the investigator using the following question:

Is there a reasonable possibility that the unsolicited AE may have been caused by the study intervention?

YES : There is a reasonable possibility that the study intervention

contributed to the AE.

NO : There is no reasonable possibility that the AE is causally related to

the administration of the study intervention. There are other, more likely causes and administration of the study intervention is not

suspected to have contributed to the AE.

If an event meets the criteria to be determined 'serious' (see Section 10.3.2), additional examinations/tests will be performed by the investigator to determine ALL possible contributing factors for each SAE.

Possible contributing factors include:

- Medical history.
- Other medication.
- Protocol-required procedure.
- Other procedure not required by the protocol.
- Lack of efficacy of the study intervention, if applicable.
- An error in study intervention administration.
- Other cause (specify).

There may be situations when an SAE has occurred, and the investigator has minimal information to include in the initial report to GSK. However, it is very important to record an assessment of causality for every event before submitting the Expedited Adverse Events Report to GSK.

The causality assessment is 1 of the criteria used when determining regulatory reporting requirements. The investigator may change his/her opinion of causality after receiving additional information and update the SAE information accordingly.

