10.4.2. Glossary of terms

Adverse event:

Any untoward medical occurrence in a patient or clinical investigation participant, temporally associated with the use of a medicinal product, whether or not considered related to the medicinal product.

An AE can therefore be any unfavorable and unintended sign (including an abnormal laboratory finding), symptom, or disease (new or exacerbated) temporally associated with the use of a medicinal product. For marketed medicinal products, this also includes failure to produce expected benefits (i.e. lack of efficacy), abuse or misuse

Blinding:

A procedure in which 1 or more parties to the study are kept unaware of the intervention assignment in order to reduce the risk of biased study outcomes. The level of blinding is maintained throughout the conduct of the study, and only when the data are cleaned to an acceptable level of quality will appropriate personnel be unblinded or when required in case of a serious AE.

In a single-blind study, the investigator and/or his staff are aware of the intervention assignment but the participant is not.

In a double-blind study, the participant, the investigator and sponsor staff who are involved in the treatment or clinical evaluation of the participants and the review or analysis of data are all unaware of the intervention assignment.

Caregiver:

A 'caregiver' is a person who has a continuous caring role for a participant or may be a person having substantial periods of contact with a participant and/or is engaged in his/her daily health care (e.g. a relative of the participant including family members or friends).

In the context of this study, a caregiver can be appointed by the participant to oversee and support the participant's compliance with protocol-specific procedures (such as transcribing responses to diaries, receiving phone calls, planning study visits, etc.). However, at no time, the caregiver should evaluate the participant's health status while answering diaries or make decisions on behalf of the participant.

217131 (RSV OA=ADJ-009) Protocol Final

Certified copy: A copy (irrespective of the type of media used) of the

original record that has been verified (i.e. by a dated signature or by generation through a validated process) to have the same information, including data that describe the context, content, and structure, as the

original.

Eligible: Qualified for enrolment into the study based upon strict

adherence to inclusion/exclusion criteria.

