- The number and percentage of participants with any unsolicited AEs during the 30-day follow-up period (i.e. the day of vaccination and 29 subsequent days) with its exact 95% CI will be tabulated by group and by Medical Dictionary for Regulatory Activities (MedDRA) preferred term. Similar tabulation will be done for Grade 3 unsolicited AEs, for any causally related unsolicited AEs, for Grade 3 causally related unsolicited AEs and for unsolicited AEs resulting in a medically attended visit. The verbatim reports of unsolicited AEs will be reviewed by a physician and the signs and symptoms will be coded according to the MedDRA. Every verbatim term will be matched with the appropriate Preferred Term.
- The number and percentage of participants with at least one report of SAE classified by the MedDRA Preferred Terms and reported after vaccine administration (Day 1) up to study end (6 months after vaccination) will be tabulated with exact 95% CI.
- The number and percentage of participants with at least one report of causally related SAE classified by the MedDRA Preferred Terms and reported after vaccine administration (Day 1) up to study end (6 months after vaccination) will be tabulated with exact 95% CI.

- The same tabulation will be presented for fatal SAEs.
- All SAEs will also be described in detail in a tabular listing.
- All pIMD will also be described in detail in a tabular listing.
- All AEs/SAEs leading to study/intervention discontinuation from dose 1 up to study end will be tabulated.
- The percentage of participants with at least one report of pIMD classified by the MedDRA Preferred Terms and reported after vaccine administration (Day 1) up to study end (6 months after vaccination) will be tabulated with exact 95% CI. The percentage of participants with at least one report of related pIMD classified by the MedDRA Preferred Terms and reported after vaccine administration (Day 1) up to study end (6 months after vaccination) will be tabulated with exact 95% CI.
- The number and percentage of participants using concomitant medication (any medication and any antipyretic) during the 4-day and the 30-day follow-up period after the study dose will be tabulated with exact 95% CI.
- Compliance in completing solicited events information will be tabulated after the study dose.
- Some of the key safety analysis will be generated by age group at first vaccination  $(60-69, 70-79, \ge 65, \ge 70 \text{ and } \ge 80 \text{ years})$  as mentioned below.

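### Investigators may receive the by-lot Day 31 report before some Month 6 contacts, which could unblind them to lot for some participants while safety is still being assessed

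*Protocol*

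**What the plan says.** Protocol section 6.3.4 keeps the study double-blind up to the final analysis, "beyond which the study will be considered single-blind". By section 9.4.1 this final analysis is the Day 31 one. It is run when the immunogenicity data for the primary endpoint are complete, and a separate end-of-study analysis follows after Month 6. For these Day 31 results, section 6.3.4 then says that "the investigators will receive a copy of the Clinical Study Report (CSR) with results of the final analyses on immunogenicity and safety data", and draws the consequence itself: "the investigators could become unblinded to some specific participants through summary results". Individual listings and assignments are held back from investigators until the Month 6 contact is complete. Section 10.1.6 adds that "GSK will provide the investigator with the randomization codes for their site only after completion of the full statistical analysis". The glossary (section 10.4.2) explains the label: "In a single-blind study, the investigator and/or his staff are aware of the intervention assignment but the participant is not".

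SAP section 4.1.1 presents immunogenicity and safety by group, and section 4.3.2.2 breaks unsolicited events down by group and preferred term. SAEs and pIMDs are collected for six months from vaccination (protocol section 10.3.7.1). Section 10.3.8.2 states: "The investigator must assess the relationship between study intervention and the occurrence of each unsolicited AE/SAE using clinical judgment". One of the Month 6 tables in SAP section 4.3.2.2 is: "The number and percentage of participants with at least one report of causally related SAE classified by the MedDRA Preferred Terms". A similar table covers related pIMDs.

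On oversight, protocol section 10.1.5 says: "Safety oversight will be provided by a blinded SRT composed of GSK RSV OA project team members". Section 6.3.4 unblinds the central study team at the final analysis and names the Safety Representative as one of its members.

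**The concern.** The trial exists to show that three lots behave alike, so lot is the assignment that the blind protects. A by-lot table of single preferred terms can reveal lot without any listing or code: the investigator who reported the only case of a term sees which column it falls in. The participants exposed this way are mainly those with uncommon events.

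The percentages with SAEs and with pIMDs up to Month 6 are stated secondary endpoints. They depend partly on investigator judgement. The investigator decides whether a disease not on the list counts as a pIMD (section 10.3.5.1), assesses causality, and may revise that opinion later (section 10.3.8.2). If the report arrives during follow-up, an investigator could make these judgements knowing a participant's lot and having seen the lots' Day 31 results. Nothing in either document says why sites need by-lot tables before follow-up ends.

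**Working it through.** **1. The plan's own figure.** The only design figure is the power, and this point does not depend on it. For one non-inferiority test with 225 per group, SD 0.45 and a limit of 1.5: SE = 0.45 × √(2/225) = 0.0424; log10(1.5)/SE − 1.96 = 0.1761/0.0424 − 1.96 ≈ 2.19; beta = 1.42%; global power = 1 − 6 × 1.42% = 91.5%. With log10(0.67) for the three lower-bound tests it is 90.9%. The stated 91% reproduces, and nothing below alters it.

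**2. Time open for each participant.** Protocol Table 2 puts Visit 2 at 30–42 days and the Month 6 contact at 180–210 days after Visit 1.
- Shortest gap: 180 − 42 = 138 days.
- Longest gap: 210 − 30 = 180 days.
- Planned gap: 180 − 30 = 150 days.

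**3. Share still awaiting Month 6 when the report reaches sites.** This needs two durations that the documents do not give: the enrolment period E, and the lag L from the last Visit 2 to release. As an assumption, take uniform enrolment over E days, Visit 2 at day 30 and Month 6 at day 180. A participant enrolled on day u is still open if u + 180 > E + 30 + L. The share is therefore (150 − L)/E, limited to the range 0 to 1.

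| E (days) | L = 30 | L = 60 | L = 90 | L = 120 | L = 150 or more |
|---|---|---|---|---|---|
| 30 | 100% | 100% | 100% | 100% | 0% |
| 60 | 100% | 100% | 100% | 50% | 0% |
| 90 | 100% | 100% | 67% | 33% | 0% |
| 120 | 100% | 75% | 50% | 25% | 0% |
| 180 | 67% | 50% | 33% | 17% | 0% |

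The answer runs from nobody to everybody. If the allowed windows replace the planned days, the lag after which the last-enrolled participant is no longer open moves from 150 to between 138 and 180 days.

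**4. Who could be identified.** In a group of about 250, a term reported once appears as 1/250 = 0.4% in one column and zero in the other two. That tells the reporting site the participant's group, and Table 6 of the protocol ties each group to one antigen lot and one adjuvant lot. The documents give no expected event counts, so the number of such participants cannot be calculated.

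**5. What one changed judgement would do.** Moving one participant into or out of a related-SAE or related-pIMD row changes that lot's percentage by 0.4 points.

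**6. What is out of reach.** The primary endpoint is the Day 31 IgG concentration, measured by a laboratory blinded to lot (section 6.3.4). It is complete before the report can exist, so its estimate, type I error and power do not change.

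**The case against.** The strongest reply is that this is a disclosed and bounded choice. The protocol calls the later period single-blind and does not promise investigator blinding to Month 6. All three groups receive the same formulation, so investigators already know that every participant received the vaccine. Causality is judged against the study intervention and not against a lot, and the Month 6 tables are descriptive with no between-lot test. Causality of an SAE or pIMD must be given with the initial report (section 8.3.3), so most events to Day 31 will have been assessed before release. Section 6.3.4.2 also allows an expedited report carrying the assignment to reach investigators, and delaying the study report would not restore the blind in those cases. All of this stands, and it is why the likely bias is small. It does not close the route that section 6.3.4 concedes, because withholding listings and codes does not hide a single-count cell.

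A reader might infer more than the documents support:
- **That Month 6 safety is simply no longer blinded.** The text says investigators could become unblinded, and only for some participants; assignments, listings and codes are withheld.
- **That all follow-up after Day 31 is exposed.** The analysis waits for the last participant's Visit 2 and assay result, and the report must then be written. No date is given. Section 6.3.4 only implies that release may come before study end.
- **That sections 6.3.4 and 10.1.6 conflict on releasing assignments.** Each sets an earliest time, and waiting for the later one satisfies both.
- **That the Safety Review Team is contradicted outright.** No section says its members are the central study team or that the Safety Representative sits on it. The overlap is an inference, so it calls for clarification.

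**Conclusion.** The point holds in a limited form. The plan allows by-lot Day 31 results to reach investigators possibly before some participants' Month 6 contact. SAE and pIMD reporting and causality by lot may then not be investigator-blinded for some participants, mainly those with a preferred term reported only once. The share still in follow-up at release is anywhere from 0% to 100%, depending on enrolment and report dates that are not given and on the uniform-enrolment assumption. The number who could be identified is unknown, and one altered judgement moves a lot's percentage by 0.4 points. Any effect is probably small and confined to descriptive secondary safety endpoints. The Day 31 consistency result is unaffected. The change is worth making because it removes an admitted route to unblinding at little cost; the validity of the primary conclusion does not depend on it.

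**What to change.** In protocol section 6.3.4, state that the by-lot Day 31 report goes to sites only after the last Month 6 contact and the freeze of the Month 6 safety data. If sites need results sooner, send only the GMC ratios and safety pooled over the three lots. Make an exception where regulation requires an investigator signatory to have access to the tables, as section 10.1.6 foresees.

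In section 10.1.5, state whether the Safety Review Team remains blinded to lot after the Day 31 analysis, given that section 6.3.4 unblinds the central study team including the Safety Representative. If the by-lot report is released early after all, describe the later safety data as single-blind in the end-of-study report.

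The cost is wording, and a report that reaches sites some months later. The sponsor's Day 31 analysis and its preparation of the report go ahead as planned, with no extra data or participants. Stating the team's status takes one sentence. Keeping the Safety Representative blinded would be a larger step, because that role is among those unblinded to prepare the report and the work would have to be reassigned.
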